Participants will be assisted with downloading the appropriate app, provided instructions on how to use the app (*iCaminemos Juntas!* or *World Walking*), and encouraged to use the app daily.

6-week interim assessment: Participants will complete interim assessments of initial changes. An invitation email and text messages containing a link to the interim surveys along with their unique password (PIN number) will be sent. Participants will complete the web-based surveys using either their computer or smartphone; no in-person meeting will be required. Participants who do not complete the surveys within 3 days will receive an email and text reminder (and 3 more reminders at 3-day intervals if still not completing it).

12-week post-test assessment: Participants will complete an in-person post-test assessment. They will meet individually with a study staff to complete the online surveys on a study tablet and a brief post-test interview.

3C.6.2. Outcomes: Baseline, Interim, and Post-test Measures. The baseline, 6-week interim, and 12-week post-test surveys will use validated scales to measure the primary outcome – physical activity - and secondary outcomes of social and environmental support and quality of life (QOL). Surveys should take 30-45 minutes to complete. See **Table 4** for schedule of measurements.

TABLE 4: Schedule of Measurements

Assessment	Screening	Pre-test/Baseline	Week 6	Week 12/Post-test
Inclusion Screener	X			
Physical Activity		X	X	X
Social & Environmental Support		X	X	X
Quality of Life (QOL)		X	X	X
Usage Data (iCaminemos Juntas! app only)			X	X
System Usability Scale (iCaminemos Juntas! app only)				X

Physical Activity:

The Community Healthy Activities Model Program for Seniors (CHAMPS¹⁶⁰) is a 41-item PA questionnaire that measures self-reported minutes-per-week of PA calculated as total weekly caloric expenditure in all PA. It was developed for underactive populations and validated among older adults.¹⁶⁰ However, CHAMPS has been used with younger and racially/ethnically diverse populations; it is sensitive to change specifically in Latino and other populations including ones younger than senior age.¹⁶⁴⁻¹⁶⁷ The CHAMPS asks about activities undertaken for exercise, daily activities that are physical in nature, and physically active recreational activities during “a typical week in the past 4 weeks.” CHAMPS has strong psychometric properties,^{160,168} including validation in Spanish and sensitivity to change.¹⁶⁹⁻¹⁷¹

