***iCaminemos Juntas!* only measures:**

Accelerometry and App Usage: Better understanding of the feasibility, accuracy, and added value of accelerometry will inform commercialization efforts. Fitbit® devices will monitor PA for participants who own that device. The Fitbit® will automatically record daily step data in the *iCaminemos Juntas!* app and progress towards the steps/day goal will be graphically presented on the app, using a color-coded graph automatically sent to the participant's phone. For participants who do not own a Fitbit®, the phone's built-in GPS will record the route walked. Data on the time spent during the walk plus the distance derived from the GPS and the walking pace provided by the user in her profile will be combined to estimate steps. *iCaminemos Juntas!* participants will also enter other exercise activities (non-*Caminemos* walks) (minutes/day) using the app. User-entered data will be compared to PA data gathered using the Fitbit® or LBS distance tracking feature.

App usage will be measured by having participants register on the server when downloading the *iCaminemos Juntas!* app. The server will record the number of times (date and time) the app connects to the server and users use various app features (number of uses, initiating walks, accepting walks, app tools used, etc.). Ecological momentary assessment (EMA) will be utilized to evaluate the app's ease of use. EMA's repeated sampling of experiences and behaviors in real time at random intervals should minimize recall bias and increase ecological validity,¹⁸⁸⁻¹⁹⁰ highlight individual differences in behavior and distribution over time, and detect factors affecting behavior.¹⁹¹⁻¹⁹⁵ EMA will be used to assess level of interest and likability of the *iCaminemos Juntas!* app. Participants randomized to that condition will be sent "push notifications" via the app once a week at various times of day that ask them to rate their opinions on the app. Users will also evaluate the app on the System Usability Scale at the 12-week post-test.¹³⁴

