3C.6.3. *iCaminemos Juntas!* Intervention (n=100). A description of the *iCaminemos Juntas!* app was provided in **Section 3C.4.** Participants will download the app following the procedures outlined in **Section 3C.7.1.** Project staff will provide *iCaminemos Juntas!* users a one-one-orientation to the app and how to use its unique features. Daily alerts and notifications will engage users in daily use of the app and provide up-to-date information on users' progress. Participant responses will also be used to evaluate additional or on-going support of users' needs (e.g., increase/ decrease prompts based on user preferences, tailored messages around a set goal, etc.). To protect privacy and to ensure that the participant is the person completing the app activities, KB will uniquely identify the user's smartphone based off the device's "hardware footprint". The app will upload all app activity data to the KB secured web server database.

3C.6.4. World Walking App Comparison Group (n=100). *World Walking* (www.worldwalking.org) is an app available for free on both iOS and Android platforms.¹⁹⁶ It allows users to track walking steps using the phone's LBS features, display walks on a virtual route, create virtual walking groups (you and other users can have shared goals for walking a certain distance such as walking the Great Wall of China), chat with virtual group members, earn badges for meeting goals, connect to Fitbit, and receive push notifications. There are a number of similarities between the two apps; participants will be able to track their walking, have a reward-based system for meeting goals, map their walks, use Fitbit, and have a social network component. The app encourages social interaction by letting walkers form virtual clubs, working together to meet distance targets.

However, while there are similarities between the two apps, *World Walking* will not allow for real-time, in-person social connection (meeting other women in-person and walking locally), or connection to social media.

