Data security: KB's server farm has 5 Dell PowerEdge servers with two 3.2 Ghz Xeon processors, four with 32 gigabytes of RAM and one with 64 gigabytes, and three 1 Terabyte hard drives that operate off a hardware RAID5 system, connected to a local area network (LAN) running the Windows 2008 or 2012 operating system and to the Internet through a 20-megabyte Fiber connection. KB programmers monitor and maintain all programs and databases. Sensitive information is protected by a hardware firewall (Cisco ASA 5505) and each server has its own native Windows security software. All KB servers are connected via 1 Gigabit high-speed switched network, ensuring high-speed transfer between machines. All networked computers are protected from viruses by Sunbelt Vipre Enterprise. Nightly backup of each computer protects against the loss of data.

3C.8. Statistical Power Calculations and Analysis.

Sample size: We expect results similar to those previously revealed in a study by Co-I, [name].²⁰² In that study, participants in a peer mentor arm reported an average increase of moderate-to-vigorous physical activity of 216.2 minutes/week ($SD = 355.7$) from baseline to 12 months compared to a 178.0 minutes/week ($SD = 234.9$) increase among those in the comparison arm. The comparison arm increased an average of 71.5 minutes/week ($SD = 179.1$) from baseline to 12 months. Comparing the two arms, with a change of 71.5 minutes/week, shows sample sizes of 81 and 81 achieve 90% power to reject the null hypothesis of equal means when the population mean difference is 144.7 with standard deviations of 355.7 for peer mentor arm and 179.1 for the comparison arm, and with a significance level (alpha) of 0.05 using a two-sided two-sample unequal-variance t-test. Adjusting for a conservative level of dropout at 20% allows for 100 per group for a total sample size of 200. If our active arm is similar to the comparison arm, because of the smaller standard deviation, the sample size necessary to achieve 90% power only increases to 82 per group, despite the lowered difference.

Analyses:

There 3 specific aims that will be evaluated. The analyses for Aims 1 and 2 are heavily descriptive in nature. Means (standard deviations), medians (Interquartile range), distributions, frequencies and percentiles, etc. will be used to characterize the outcome measures.

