Aim 1 will be assessed by examining the number of connections/matches for walking (creating and/or joining a walk). We believe that at least 70% of the *iCaminemos Juntas!* intervention group will establish at least one connection and participate in at least one walk (e.g., 78% of users in Phase I created at least one walk). The distribution of number of connections and walks completed will be examined. We will test whether there is a difference between the groups in connections that occurred using a chi square test and will further test a single proportion that the *iCaminemos Juntas!* group will have significantly more than 70% active participation as evidenced by making at least 1 connection.

Aim 2 will be evaluated descriptively and via feasibility testing showing that location-based services can be replicated regardless of region.

Aim 3 is critical to product development and will evaluate whether *iCaminemos Juntas!* increases physical activity, social support, and quality of life (QOL) in Latinas. Three hypotheses for the comparative-effectiveness trial will be examined:

H₁: Latinas randomized to the *iCaminemos Juntas!* app will report greater improvements in their physical activity compared to Latinas randomized to the comparison app (*World Walking* app) at 12-weeks post-test.

H₂: Latinas randomized to the *iCaminemos Juntas!* app will report greater increases in their social support for exercise compared to Latinas randomized to the comparison app at 12-weeks post-test.

H₃: Latinas randomized to the *iCaminemos Juntas!* app will report greater improvements in their quality of life (QOL) compared to Latinas randomized to the comparison app at 12-weeks post-test.

Additional secondary analyses will (1) evaluate immediate changes in the PA, social and environmental support, and QOL measures at 6 weeks; (2) assess mediators at 6-weeks for a mediational analysis on 12-week outcomes; and (3) evaluate app usage data (e.g., number of log-ins, number of “check-ins”, EMA responses for likability and satisfaction with the app).

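### Aim 1's between-arm chi-square on walking connections has no valid comparator, because a connection is a function of the test app and usage data are collected for that app only

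*Combined protocol and SAP*

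**What the plan says.** Section 3C.8 introduces the analyses with the remark "The analyses for Aims 1 and 2 are heavily descriptive in nature". For Aim 1 the outcome is the number of walking connections, defined as creating and/or joining a walk. The plan expects that at least 70% of the "intervention group will establish at least one connection and participate in at least one walk", and cites a Phase I figure of 78% of users who created at least one walk. Two tests follow:

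- **Between arms:** "We will test whether there is a difference between the groups in connections that occurred using a chi square test".
- **Within the test-app arm:** a single-proportion test that the "group will have significantly more than 70% active participation as evidenced by making at least 1 connection".

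No alpha or sidedness is given for either test.

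On data collection, Table 4 in section 3C.6.2 lists "Usage Data ( iCaminemos Juntas! app only"), at weeks 6 and 12. The text on measures specific to that app says "App usage will be measured by having participants register on the server when downloading the" iCaminemos Juntas! app, and the server then logs the walks a user initiates and accepts. Section 3C.6.4 says World Walking "will not allow for real-time, in-person social connection (meeting other women in-person and walking locally"), although its users can "create virtual walking groups (you and other users can have shared goals for walking a certain distance") and chat with group members.

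**The concern.** A between-arm test needs an outcome that can occur in both arms and is recorded in the same way in both. Neither condition is met. A woman assigned to World Walking cannot create or join a walk as Aim 1 defines it, and the plan describes no record of what she does in her app.

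The analyst will therefore find either an empty comparator column or one filled with zeros. In the second case a significant result is almost guaranteed and says nothing about how well the test app works. It could still be quoted as support for Aim 1 when the app had fallen far short of its own 70% expectation, and section 3C.6.4 ties this phase to commercial objectives.

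**Working it through.** The plan gives no sample size, power or rate for the Aim 1 chi-square, so there is no figure to reproduce.

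**Step 1. Can the outcome occur, and is it recorded, in each arm?**

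| Question | iCaminemos Juntas! | World Walking |
|---|---|---|
| Can a walk be created or joined as Aim 1 defines it? | Yes: Create-a-Walk and Join-a-Walk are its components (3C.3.1c) | No real-time, in-person connection (3C.6.4) |
| Is usage logged? | Yes, on the sponsor's server (3C.6.2) | None described; Table 4 names the test app only |
| Does a survey in 3C.6.2 count connections? | None described | None described |

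The comparator cell is therefore missing or fixed at zero.

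**Step 2. What the test does if the cell is entered as zero.** Inputs: n = 100 per arm (3C.6.3, 3C.6.4), x test-app users with a connection, 0 in the comparator. For x/n against 0/n the uncorrected Pearson statistic reduces to 2nx/(2n − x), and the two-sided Fisher p to 2·C(100, x)/C(200, x).

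| x/100 vs 0/100 | Pearson chi-square | Pearson p | Fisher p |
|---|---|---|---|
| 3 | 600/197 = 3.05 | 0.081 | 0.246 |
| 4 | 800/196 = 4.08 | 0.043 | 0.121 |
| 5 | 1000/195 = 5.13 | 0.024 | 0.059 |
| 6 | 1200/194 = 6.19 | 0.013 | 0.029 |
| 70 | 14000/130 = 107.7 | 3e-25 | far below 0.001 |

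The smallest significant count is 4 (Pearson) or 6 (Fisher). The same counts apply with 80 per arm, that is, after the planned 20% dropout.

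**Step 3. How often the test would be significant in an app that failed.** With X ~ Binomial(100, p):

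- true rate 10%: P(X ≥ 6) = 0.942 (Fisher) and P(X ≥ 4) = 0.992 (Pearson);
- true rate 20%: above 0.999 for both.

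**Step 4. The single-proportion test, which needs no comparator.** Exact binomial against 0.70 with n = 100. Alpha and sidedness are my assumptions, because the plan gives neither.

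| Assumed level | Count needed | Actual size | Chance of passing at true 78% | at true 82% |
|---|---|---|---|---|
| One-sided 5% | 78/100 | 0.048 | 56% | 88% |
| Upper tail 2.5% | 80/100 | 0.016 | 37% | 75% |

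At the Phase I figure of 78% the test is close to a coin toss or worse. Non-rejection would not show that the 70% expectation was missed. The expectation also covers a connection and a walk, whereas the test covers a connection alone.

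**Step 5. Precision of a descriptive report.** Clopper-Pearson 95% limits: 70/100 gives 60% to 79%; 78/100 gives 69% to 86%.

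**The case against.** The strongest reply is that little hangs on this test. Aim 1 is declared largely descriptive, and the plan also reports the distribution of connections and walks and tests the test-app proportion against 70%. A shortfall would show beside the chi-square. That is true. It limits the harm, but it does not make the between-arm test informative.

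A second reply is that the comparator measure is undefined rather than impossible. World Walking has virtual groups and chat, section 3C.8 speaks of utilization of the apps in the plural, and the week 12 visit includes a brief interview whose content is not given. However, joining a virtual group is not creating or joining a walk, so counting it would compare different things. The plural names no data source and sits badly with Table 4, and the interview is not said to ask about connections. Reading the groups as the two cities would make the test feasible, but the plan does not say so, and the same sentence uses the word for the test-app arm.

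A third reply is that the Fisher figures are not for the test named in the plan. That is fair, but they are the conservative choice: with uncorrected Pearson the threshold falls from 6 to 4 women. All these figures assume the comparator is coded as zero; if it is left missing, the test simply cannot be run.

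**Conclusion.** The concern holds. As written, the between-arm chi-square is either impossible or uninformative. With the comparator coded as zero, an app reaching only 10% of its users would still give p < 0.05 in 94% of trials by Fisher's test and 99% by uncorrected Pearson. This rests on the plan's own definition of a connection and on the absence, in the protocol text available, of any comparator usage source.

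It should be corrected, but it does not threaten the trial's main conclusions: the primary outcome, H1 to H3 and the sample size do not depend on it. The gaps in the single-proportion test (alpha, sidedness, endpoint) are a lesser matter.

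**What to change.** Delete the between-arm chi-square on connections. Suggested replacement:

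> Among all women randomised to iCaminemos Juntas!, we will report the number and percentage with at least one connection (a walk created or joined) and, separately, the number and percentage with at least one connection and at least one walk, each with an exact 95% confidence interval. No between-arm test of connections will be done.

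State the expected precision from Step 5. If the sponsor wants a between-arm comparison, ask the same self-report item on walking with others in both arms.

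Keeping the single-proportion test is the sponsor's choice. If it stays, state its alpha and sidedness and whether the endpoint is a connection alone or a connection plus a walk. Add that non-rejection does not mean the 70% expectation was missed. The reference to utilization of both apps in section 3C.8 should be reconciled with Table 4.

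The cost is analysis-plan wording only, plus one item in the existing survey if the optional comparison is wanted.

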The goal of *iCaminemos Juntas!* is to connect Latinas with one another near their neighborhood to encourage increased PA partnerships (e.g., walking). Connections between registered app users will be accomplished through push/pull technology. Push/pull technology describes a style of internet and LBS-based communication where an information transmission request (e.g., "I am interested in going for a walk...is anyone else?") can be initiated by the app user (i.e., "pull") or by the app (i.e., "push"; e.g., a notification sent to an app user indicating that someone would like to walk). Women who are interested in going for a walk can send a request to all other registered app users through the *iCaminemos Juntas!* app. Women who receive a push notification can decline or accept the request. Using LBS, *iCaminemos Juntas!* identifies each assenting user's location and, using LBS algorithms, triangulates each user to one another. Next, using publicly-available geographic information systems (GIS) and LBS data sources,¹⁴²⁻¹⁴⁴ the app determines the location of nearby PA resources (e.g., parks, recreation centers, etc.) that are the best proximal match for the identified users. Users are sent a push notification and map of the PA location. The app requests the user to confirm or decline meeting at this location and sends a meeting location and time confirmation. Using LBS, the app is able to determine whether the user arrived at the designated location. At the user's preferred contact time, the app sends a push notification asking the user to answer four questions: (1) Did you meet a *iCaminemos Juntas!* partner?; (2) Did you walk today?; (3) How long did you walk?; and (4) Did you find the location safe?

The app gathers user profile information, PA preferences, and walking goals. Time- and location-specific notifications are the app's foundation, connecting users and influencing theoretical constructs (e.g., conscious raising, social support) to increase PA. Benefits of using a mobile app include an instantly available source of

social support once a user creates an account, convenience and ease of use, and geographically-relevant information tailored to the user. To ensure users' privacy and safety, the app serves as the "gatekeeper:" Users cannot be located by another user without permission and cannot set up meetings to walk with an unauthorized user. All participants will be fully informed of these privacy policies.

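### The Aim 1 test against 70% counts one connection only, while the stated expectation is a connection and a walk, so a significant result would not support that expectation

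*Combined protocol and SAP*

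**What the plan says.** All the key wording is in section 3C.8, Analyses, Aim 1.

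- **Measure:** the "number of connections/matches for walking (creating and/or joining a walk" (the parenthesis closes there).
- **Expectation:** at least 70% of the intervention group "will establish at least one connection and participate in at least one walk".
- **Support offered:** "78% of users in Phase I created at least one walk".
- **Description:** "The distribution of number of connections and walks completed will be examined".
- **Formal test:** a single proportion, to show "significantly more than 70% active participation as evidenced by making at least 1 connection".

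The description of how the app connects users, just before section 3C.3.1, says: "Women who receive a push notification can decline or accept the request". It adds that "the app is able to determine whether the user arrived at the designated location", and that the app later asks each user whether she met a partner and whether she walked that day. Under section 3C.6.2 (the measures for the app arm only), the server logs starting a walk and accepting a walk as separate actions.

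**The concern.** The expectation and the test share the 70% threshold but not the event. The expectation needs two things from each woman; the test needs one. Anyone who meets the joint condition also meets the tested one, but not the reverse. The tested proportion can therefore only equal or exceed the proportion of interest, and a significant result gives no assurance about the latter.

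The gap may be wider if creating a walk is enough to count as a connection. The and/or in the gloss allows that reading, and the benchmark cited is itself a creation rate. A woman whose request is declined by everyone could then count as an active participant. Even if a connection needs a second person, a woman who accepts a walk and does not go still counts.

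At stake is the engagement claim for the app: that most users connected and walked. Section 3C.6.4 names real-time, in-person connection as a feature the comparator lacks, so the claim should rest on an endpoint that includes walking.

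**Working it through.** **1. The events side by side (section 3C.8, Aim 1)**

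| Role in the plan | Connection required? | Walk required? |
|---|---|---|
| Stated expectation, at least 70% | yes | yes |
| Test against 70% | yes | no |
| Phase I evidence, 78% | creation only | no |

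The last row is supporting evidence, not a second endpoint, but it speaks only to creation.

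**2. Does the plan treat connecting and walking as one thing?** No. The Aim 1 text lists connections and completed walks as separate quantities. Later in 3C.8, noncompliant women are described by not walking and/or not forming connections. A woman who connects but never walks could be noncompliant there and an active participant in the Aim 1 test.

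**3. The plan's own figures.** No sample size, power, level, sidedness or denominator is given for this test. The powered calculation in 3C.8 (81 per arm, 90% power) is for physical activity. It reproduces (Welch power 90.03% at 81) but does not bear on this point.

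**4. Cut-off for the test.** Inputs: n = 100 in the app arm (3C.6.3) and null value p0 = 0.70 (3C.8). The one-sided level is my assumption, 0.05 or 0.025. The cut-off r is the smallest count with P(X ≥ r | n, p0) at or below the level, X binomial.

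- One-sided 0.05: P(X ≥ 77) = 0.0755 and P(X ≥ 78) = 0.0479, so r = 78.
- One-sided 0.025: P(X ≥ 79) = 0.0288 and P(X ≥ 80) = 0.0165, so r = 80.

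Changing the endpoint leaves the cut-off alone. It changes who counts as a success.

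**5. Effect of adding the walk.** Let c be the proportion who make a connection and q the share of those who go on to walk. The joint rate is c × q, and the chance of passing is P(X ≥ r | 100, c × q). I take c = 0.78, borrowing the Phase I creation rate. The value of q is assumed, because the documents give none.

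| q | joint rate 0.78 × q | pass, r = 78 | pass, r = 80 |
|---|---|---|---|
| 1.0 | 0.780 | 0.557 | 0.366 |
| 0.9 | 0.702 | 0.052 | 0.018 |
| 0.8 | 0.624 | 0.0006 | 0.0001 |
| 0.7 | 0.546 | below 0.0001 | below 0.0001 |

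The first row is also the chance of passing the test as now written, if the rate of creating or joining is 78%.

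**6. Sensitivity to c.** Women who only join also count, so c could exceed the creation rate. With c = 0.90 and r = 80, the chance of passing is 0.999 at q = 1, 0.657 at q = 0.9 (joint rate 0.81) and 0.044 at q = 0.8 (joint rate 0.72).

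**7. Sensitivity to the denominator.** With 80 women analysed (20% attrition, 3C.6.5) the cut-offs are 64 and 65. At 78% the chance of passing is 0.392 or 0.292; at 70.2% it is 0.033 or 0.018.

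**The case against.** The strongest reply is that this is a wording slip in an aim about building the app. Section 3C.8 calls the Aim 1 and 2 analyses mostly descriptive, attaches no go/no-go rule to this proportion, and plans to report walks completed and to study noncompliant women closely. Many connections with few walks would be visible. This stands and limits the weight of the point. It does not remove the mismatch: the plan sets a significance test against a number, and the tested event is not the expected one.

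A reader might infer more than the documents support:

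- **That an unanswered post definitely counts as a connection.** The plan does not say so. It pairs connections with matches, which suggests a second person, and the parenthesis may only name two routes to a match. The and/or and the creation-based 78% point the other way. The term is ambiguous.
- **That there are three rival responder definitions.** There are two. The Phase I figure is given as an example in support.
- **That the test will pass easily on app clicks.** At the one rate the documents give, 78%, the lenient test passes with probability 0.37 or 0.56, depending on the level. A sharp contrast between an easy pass and a near-certain failure appears only with chosen inputs.
- **That the trial's main conclusion is at risk.** The primary outcome is self-reported physical activity under Aim 3, which this proportion does not enter.

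**Conclusion.** The mismatch holds on the text and needs no assumption: the 70% expectation is joint, the 70% test is not, and passing the test would not establish the expectation. That a created but unaccepted walk counts is a plausible reading, which one sentence in the plan could settle. The 78% from Phase I supports the creation step only.

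The numerical size is illustrative. It rests on an assumed one-sided level, on the Phase I creation rate standing in for the connection rate, and on an unknown follow-through rate. On those terms, a shortfall of 10% in follow-through takes the chance of passing at one-sided 0.05 from 0.56 to about 0.05; with a higher connection rate the loss is smaller. The point is worth correcting before data are seen, but it concerns a secondary, largely descriptive aim.

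**What to change.** In section 3C.8, Aim 1:

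1. Define a connection as a created or joined walk accepted by at least one other user.
2. Test the stated joint endpoint: at least one connection and at least one completed walk. Completion could be a yes to the post-walk question on whether she walked, tied to that walk. Location-verified arrival should support this answer, not replace it, because arriving does not show that she walked. Do not also require that a partner was met unless the expectation is rewritten, since it asks only for participation in a walk.
3. Use all women randomised to the app as the denominator. State the level, the sidedness and how an unanswered post-walk question is counted.
4. Report the created, joined, matched and walked rates descriptively, and set the Phase I 78% beside the created rate only.

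The cost is a change of wording and a different query on data the app already records, plus a rule linking the answer, which refers to the day, to a particular walk. The reported participation rate and the chance of passing the 70% test will both be lower, by an amount that depends on follow-through.
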